## 8.4 Primary and Secondary Endpoints and Associated Hypotheses

### 8.4.1 Primary Endpoint and Associated Hypotheses

No formal hypotheses are specified for this study. The study endpoints are representative of endpoints that are currently reported in the available literature for stapler performance and this will allow for qualitative comparisons with the results from this study.

The primary performance endpoint in this study is the percentage of subjects who experienced a failure of the ECHELON CIRCULAR™ Powered Stapler to perform per its IFU. This includes but is not limited to difficulty placing or removing the stapler, stapler misfire/failure of the device to fully fire, staple line defects, incomplete or thin donuts, tissue damage, positive intraoperative leak test, detached components, unformed staples, or any other device failures.

The denominator for the primary endpoint will be the total number of subjects where an anastomosis was attempted and the numerator will be the number of subjects who experienced a stapler performance issue. An exact 95% confidence interval using the Clopper-Pearson method will also be estimated.

### 8.4.2 Secondary Endpoints and Associated Hypotheses

Summary statistics will be provided for the Surgery Task Load Index (Surg-TLX). Surgeons are asked to rate 6 specific components after each surgery performed. The 6 components are – mental fatigue, physical fatigue, hurried/rushed pace, procedure complexity, anxious while performing procedure, and distracting operating environment. Each component is scored on a 0 to 100 scale with lower scores representing a ‘Low’ response on that component and higher scores indicating a ‘High’ response on that component. Summaries will also be provided for an overall score which is calculated as the average of the six components for each surgery.

Counts and percentages will be provided for responses to the surgeon satisfaction questionnaire.

#### 8.4.3 Additional Endpoints

Counts and percentages will be provided for results of the intra-operative leak test. The requirement for any blood transfusion and reason of the transfusion will be summarized with counts and percentages. Summary statistics will be provided for length of stay and discharge details will be listed. All protocol deviations recorded during the study will be classified as minor or major. Counts and percentages will be provided for the type of deviation, the rationale for the deviation, and classification (minor or major). As indicated in Section 3.19 of the protocol, photos of the anastomotic donuts were to be taken if possible. These photos were to be reviewed and assessed by the Sponsor to evaluate the quality of the donuts created and determine if either donut appeared thin or incomplete. No summary analyses were planned for the results of these assessments in the protocol and none are specified here. The results of the Sponsor assessment will be listed.

### 8.5 Safety Analyses

Safety will be assessed through the incidence of AEs and SAEs, which will be coded using the Medical Dictionary for Regulatory Activities (MedDRA). The number and percentage of subjects reporting AEs and SAEs will be summarized at the MedDRA system organ class and preferred term level. Similar summaries will also be provided for AEs and SAEs related to the study device, as well as for AEs and SAEs related to the study procedure. Related events are those where the relationship is indicated as Unlikely, Possibly, Probably, or Causal. Summaries will also be provided for AEs, device-related AEs and SAEs where the start date of the event is equal to the day of surgery (intraoperative AEs). Similar summaries will be generated for AEs and device-related AEs where the start date of the event is strictly after the day of surgery (postoperative AEs). All reported adverse events will be listed. Listings will also be provided for concomitant procedures and concomitant medications.

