### **Relationship of Adverse Events**

It is the Investigator's responsibility to assess the relationship between all AEs and the study procedure or circular staplers used in the study. Only AEs attributable (relationship of possibly, related, or unknown) to a device or the study procedure are to be recorded in the eCRF and reported to the Sponsor.

The following guidelines should be used in determining the relationship of an adverse event to a device, study procedure, or other causality:

- **Possibly** – A clinical event (including abnormal laboratory result) that presents an unlikely association between device/procedure, which cannot be ruled out with certainty, but could also be explained by alternative etiology;
- **Related** – A clinical event (including abnormal laboratory result) that presents a strong temporal relationship between device/procedure, in which an alternative etiology is unlikely; or
- **Unknown** – A clinical event (including abnormal laboratory result) that cannot be determined to be related or unrelated to device/procedure given the information obtained.

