## **7.2 REPORTING PROCEDURES FOR ADVERSE EVENTS**

### **7.3 RECORDING ADVERSE EVENTS**

The Investigator will record all device- or procedure-related AEs considered attributable (relationship of possibly, related, or unknown) to the powered circular stapler or to the procedure in the source documents and associated eCRF. The site must complete the AE CRF within two weeks of becoming aware of an event and SAE eCRF within 72 hours of becoming aware of the event. Supporting SAE documentation should be de-identified and emailed to the Clinical Study Lead.

Standard medical terminology should be used when recording AEs. In addition, the following information should be recorded:

- Onset Date
- Resolution date or date of death
- Severity of the event
- Action Taken
- Event Status (ongoing at study end or resolved)
- Relationship of AE to a surgical device used in the study
- Relationship of AE to the study procedure
- Indication of whether the event is serious

Data related to SAEs will be collected until event resolution, or until the event is considered stable, or until all attempts to determine the resolution of the event are exhausted. All AEs that are unresolved at study completion (or early termination) will be recorded as ongoing at study end.

The Investigator will be required to assess if the SAE is considered anticipated (Appendix II) and if the event involved a product complaint. The report of an SAE by a site does not constitute an admission that study personnel or the user facility (hospital/clinic) caused or contributed to the event. The study site is also responsible for submitting to the reviewing IRB/EC according to their IRB/EC procedures.

The Investigator will be required to assess if the SAE is considered anticipated (Appendix II) and if the event involved a product complaint. The report of an SAE by a site does not constitute an admission that study personnel or the user facility (hospital/clinic) caused or contributed to the event. The study site is also responsible for submitting to the reviewing IRB/EC according to their IRB/EC procedures.

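### SAP 8.5 picks out related adverse events by causality labels that differ from those in protocol 7.1 and 7.3; only Possibly is on both lists, and Unknown has no SAP counterpart

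*SAP*

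**What the plan says.** **Protocol.** Section 7.1, under Relationship of Adverse Events, limits recording by causality label: "Only AEs attributable (relationship of possibly, related, or unknown) to a device or the study procedure are to be recorded in the eCRF". It defines three labels:

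- Possibly: an event that "presents an unlikely association between device/procedure, which cannot be ruled out with certainty" but that could have another cause.
- Related: an event that "presents a strong temporal relationship between device/procedure, in which an alternative etiology is unlikely".
- Unknown: an event that "cannot be determined to be related or unrelated to device/procedure given the information obtained".

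Section 7.3 repeats the list for events "considered attributable (relationship of possibly, related, or unknown) to the powered circular stapler" or to the procedure. It also asks for two separate items on each event: "Relationship of AE to a surgical device used in the study" and "Relationship of AE to the study procedure". Section 5.8 plans separate summaries of device-related and procedure-related events, and the same for serious events.

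**SAP.** Section 8.5 defines the subset in other words: "Related events are those where the relationship is indicated as Unlikely, Possibly, Probably, or Causal". The definition governs Tables 13 and 14 (device), 15 and 16 (procedure), and 30 and 32 (device-related events on, and after, the day of surgery). According to the SAP revision history, Tables 29 to 33 and supporting text in 8.5 were added in revision 2.0 for a registration submission. The history mentions no change of causality scale.

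**The concern.** The SAP rule is explicit, but it is not written in the labels that the protocol says are recorded. A programmer who applied it to data holding the protocol's labels would select only events rated Possibly. Events rated Related, for which the protocol regards another cause as unlikely, would drop out of the device-related and procedure-related tables. So would events rated Unknown, which the protocol counts as attributable.

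Safety surveillance is a secondary objective, and the device-related tables are where a reader looks for the device's own safety record. Two of them were added for a regulatory submission. With only the protocol and the SAP in hand, a reader cannot tell which events count as device-related.

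**Working it through.** There is no stated figure to reproduce. The check compares two label lists and traces which tables use the rule.

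**Step 1. The labels side by side.** Protocol (7.1, 7.3): Possibly, Related, Unknown. SAP (8.5): Unlikely, Possibly, Probably, Causal.

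| Label | Protocol | SAP |
|---|---|---|
| Possibly | yes | yes |
| Related | yes | no |
| Unknown | yes | no |
| Unlikely | no | yes |
| Probably | no | yes |
| Causal | no | yes |

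Distinct labels: 3 + 4 − 1 = 6. Shared: 1.

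**Step 2. Match by definition rather than by name.** The protocol defines Possibly as an unlikely association that cannot be excluded, so it can cover the SAP's Unlikely and Possibly. Its Related can cover Probably and Causal. This matching is inferred; neither document states it. Unknown, where the relationship cannot be determined, matches none of the four SAP labels.

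**Step 3. Apply the rule under each possible state of the database.**

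- *Case A, the database holds the protocol's labels.* The rule selects Possibly only. Not selected: Related and Unknown, 2 of 3.
- *Case B, the database holds the SAP's labels.* The rule selects all four; lost: 0 of 4. Three of the four (Unlikely, Probably, Causal) have no protocol definition, and 1 of the 3 protocol categories (Unknown) has no counterpart.
- *A mixed case, the SAP's labels plus Unknown.* Events rated Unknown are not selected.

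**Step 4. Count the tables.** Adverse event tables: 11 to 16 (6) plus 29 to 33 (5) = 11. Using the rule: 13, 14, 15 and 16 (4 of the first 6) plus 30 and 32 (2 of the 5 added) = 6. Not using it: 11, 12, 29, 31 and 33 = 5.

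**Step 5. Scale of the effect (assumed counts only).** The documents give no event counts by label. Suppose 20 of the 165 planned subjects had a device-attributable event (20/165 = 12.1%), and a share *u* of them had only events whose label the rule does not select. The table would then show 20 × (1 − *u*) subjects:

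| *u* | Subjects shown | Percent of 165 |
|---|---|---|
| 0% | 20 | 12.1% |
| 10% | 18 | 10.9% |
| 25% | 15 | 9.1% |
| 50% | 10 | 6.1% |

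This shows the direction and how the loss scales. It is not an estimate for this study.

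**The case against.** The strongest reply is that the harmful case depends on a form nobody reading these documents can see, and that the internal evidence leans the other way. The SAP was written for the final analysis and is built around the eCRFs: Section 6 identifies the Full Analysis Set by a specific eCRF question, Section 8.8 names the eCRF source of each subgroup, and the appendix ties its listings to the eCRFs in use. A four-level scale found nowhere in the protocol was more likely taken from the database than invented. In that case the rule works, and it is inclusive, since even Unlikely counts as related. If the field has no Unknown option, no event can be dropped for carrying it.

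The reply also points out that safety reporting is largely protected. Protocol 7.1 has only attributable events recorded at all, so Tables 11 and 12 show every recorded event and serious event whatever its label. Listing 18 does the same, and because the appendix lists all collected fields, the split could be rebuilt.

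Much of this stands. Case B is plausible, and the effect is confined to the device and procedure breakdown. Two things remain. The protocol also says what goes into the eCRF, and says it in both 7.1 and 7.3, so the documents point both ways. And the all-event tables cannot replace the breakdown: an event is recorded if attributable to the device or to the procedure, the two relationships are separate items, and only the filtered tables separate them. SAP 8.1 does not settle the matter, because it covers final analyses that differ from the SAP, not a SAP rule that differs from the protocol.

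**Conclusion.** The concern holds and should be fixed. The mismatch is certain: one shared label out of six, no mapping in either document, and six of 11 adverse event tables governed by the rule.

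The effect on results is not certain. It rests on the eCRF response options. Under the protocol's labels, two of three attributable categories, including the strongest, would be missing from the related-event tables, so device-related and procedure-related events could be understated. Under the SAP's labels no recorded level is lost, and what remains is a documentation gap: three undefined terms, no stated place for undetermined events, and an unrecorded departure from protocol 7.1. The number of events affected cannot be determined in either case. The primary endpoint, Tables 11, 12, 29, 31 and 33, and the listings are untouched.

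**What to change.** 1. Confirm the response options of the device-relationship and procedure-relationship fields on the adverse event eCRF.
2. If they are the protocol's labels, restate SAP 8.5 so that an event is related when rated Possibly, Related or Unknown, applied to each field separately, with any not-related value excluded.
3. If they differ, add a short table that maps each recorded level, by its definition, to a protocol category or to not related. State whether an undetermined relationship counts as related, and document the departure from protocol 7.1.
4. Apply the restated rule to Tables 13 to 16, 30 and 32.

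The cost is one eCRF check, one SAP sentence or a short mapping table, and one programming condition. Counts in the six tables may change.

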### 8.6 Plans for Interim Analysis

No interim analyses were planned or performed for this study.

### 8.7 Handling of Missing Data

All summaries will be performed only on enrolled subjects and only observed data will be summarized. There will be no imputation of data for early terminated subjects or for missing data within the database.

## 8.8 Subgroup Analysis

Subgroup analyses of the primary performance endpoint are planned to be performed surgical approach (open or laparoscopic as identified on the Intraoperative Procedure eCRF) and by surgery indication (diverticulitis, neoplasm, etc identified on the Medical History eCRF).

## 8.9 Assessment of Site Homogeneity

No summaries or adjustments by study site are planned for this study.

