### **Multicenter Studies**

No adjustment for center is planned in the statistical analysis. However, center specific analyses may be conducted pending within-center sample size to understand the effect that surgeon techniques and site standard of care may have on the overall results.

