## 7 Sample Size Justification

A total of 165 eligible subjects was planned to be enrolled in up to 12 sites to ensure at least 150 subjects complete the study. No formal hypothesis was being tested in this study, thus the sample size was not statistically sized, but rather was considered sufficient for a descriptive summary of stapler performance issues through confidence interval estimation and evaluation of safety. The sample size of 165 subjects was consistent with the amount of information that was planned to be collected on the powered stapler in the original study design and provides acceptable precision for estimation of the rate of stapler performance issues. Available literature suggests that stapler performance issues are observed in 15% to 20% of subjects in whom a circular stapler is used, and a sample size of 165 subjects will provide a margin of error for a one-sided 95% confidence interval that does not exceed 5.1% for estimation of the true rate of stapler performance issues.

Further, in consideration of rare AEs that may occur, for an event that occurs at a rate of, for example, 1.5%, then in a sample of 165 subjects, the probability of observing at least 1 event is greater than 90% under a binomial probability model. Thus, this sample size provides a high probability of observing rare events if they do occur and provides reasonable assurance that the absence of such events in the study is not a result of too few subjects being studied, should none be observed.

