Colorectal carcinoma	xx (xx.x%)
Ulcerative colitis	xx (xx.x%)
Diverticulitis	xx (xx.x%)
Crohn's disease	xx (xx.x%)
Colorectal polyps or polyp syndrome	xx (xx.x%)
Other	xx (xx.x%)
Estimated Anastomosis Level	
Sigmoid colon	xx (xx.x%)
Upper rectum	xx (xx.x%)
Mid rectum	xx (xx.x%)
Lower rectum	xx (xx.x%)
Colorectal Carcinoma Clinical Stage	
Clinical T	
x	xx (xx.x%)
...	xx (xx.x%)
Clinical N	
x	xx (xx.x%)
...	
Clinical M	
x	
...	

*Programming note: Only categories actually observed in the database need to be displayed for colorectal carcinoma clinical stage*

Table 4  
Medical History  
Full Analysis Set

Characteristic	Overall (N = ##)
Smoking Status	
Current smoker	xx (xx.x%)
Former smoker	xx (xx.x%)
Never smoked	xx (xx.x%)

Table 5  
Pre-Procedure Information  
Full Analysis Set

Characteristic	Overall (N = ##)
Pre-Operation Bowel Preparation	
Yes	xx (xx.x%)
No	xx (xx.x%)
Type of Pre-Operation Bowel Preparation	
Mechanical bowel preparation	xxx
Antibiotic	xxx
Enema	xxx
Other	xxx
Pre-operative Antibiotics (IV) Administered	
Yes	xx (xx.x%)
No	xx (xx.x%)

Table 6  
Intra-Operative Information  
Full Analysis Set

Characteristic	Overall (N = ##)
Surgeon Gender	
Male	xx (xx.x%)
Female	xx (xx.x%)
Surgeon Height (cm)	
n	xx
Mean (SD)	xx.x (xx.x)
Median (Min, Max)	xx.x (xx, xx)
Surgeon Weight (kg)	
N	xx
Mean (SD)	xx.x (xx.x)
Median (Min, Max)	xx.x (xx, xx)
Surgeon Hand Length (cm)	
N	xx
Mean (SD)	xx.x (xx.x)
Median (Min, Max)	xx.x (xx, xx)
Surgeon Grip Strength (kg)	
n	xx
Mean (SD)	xx.x (xx.x)
Median (Min, Max)	xx.x (xx, xx)

*Programming note: For surgeon gender, height, weight and hand length only one summary per surgeon should be included recognizing that surgeons will perform multiple surgeries. This will be accomplished through a nodupkey sort on surgeon initials within a study site.*

Table 6  
Intra-Operative Information  
Full Analysis Set

Characteristic	Overall (N = ##)
Number of Previous Cases on Day of Procedure	
n	xx
Mean (SD)	xx.x (xx.x)
Median (Min, Max)	xx.x (xx, xx)
Procedure Duration (hours)	
n	xx
Mean (SD)	xx.x (xx.x)
Median (Min, Max)	xx.x (xx, xx)
Was the Splenic Flexure Mobilized?	
Yes	xx (xx.x%)
No	xx (xx.x%)
Number of Linear Firings	
n	xx
Mean (SD)	xx.x (xx.x)
Median (Min, Max)	xx.x (xx, xx)
Surgical approach	
Open Laparotomy	xx (xx.x%)
Hand-assisted MIS	xx (xx.x%)
Laparoscopy	xx (xx.x%)
Robotic	xx (xx.x%)
Was Anastomosis Attempted?	
Yes	xx (xx.x%)
No	xx (xx.x%)
Type of Anastomosis	
End to End	xx (xx.x%)
Side to End	xx (xx.x%)

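### The primary 95% interval assumes independent subjects; it will be too narrow if the stapler-issue rate varies between sites or surgeons, and no planned table would show that variation

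*SAP*

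**What the plan says.** - **Endpoint and interval.** SAP 8.4.1 defines the primary endpoint as a subject-level percentage pooled over the whole study: "The denominator for the primary endpoint will be the total number of subjects where an anastomosis was attempted". For precision it states: "An exact 95% confidence interval using the Clopper-Pearson method will also be estimated". No term for site or surgeon enters.
- **Sample size.** SAP 7 reads "A total of 165 eligible subjects was planned to be enrolled in up to 12 sites". It takes from the literature that "stapler performance issues are observed in 15% to 20% of subjects in whom a circular stapler is used", and claims a "margin of error for a one-sided 95% confidence interval that does not exceed 5.1" percentage points. Protocol 5.7 makes the same statement.
- **Repeated surgeons.** The SAP Appendix, in the programming note to Table 6, counts each surgeon's personal characteristics once, "recognizing that surgeons will perform multiple surgeries". It does so by surgeon initials within site, so both identifiers are in the data.
- **Site handling.** Protocol 5.8 (Multicenter Studies) plans no adjustment for center but adds that "center specific analyses may be conducted pending within-center sample size to understand the effect that surgeon techniques and site standard of care may have" (that is, for the study's findings as a whole). SAP 8.9 closes that option: "No summaries or adjustments by study site are planned for this study". None of Tables 1 to 33 is by site or by surgeon.
- **What remains visible.** SAP 8.1 lists all eCRF data per subject, and Listing 11 covers technical issues with the stapler.

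**The concern.** Clopper-Pearson guarantees its stated coverage only when each subject is an independent draw with the same probability of an issue. Several components of this endpoint plausibly depend on who operates and where: difficulty placing or removing the device, thin donuts, and a positive leak test. The surgery follows the surgeon's usual practice (Protocol 3.9), and leak assessment follows each site's own standard of care (Protocol 3.17). The SAP deals with repeated surgeons when it summarises their height, weight and hand length, but not when it computes the primary interval.

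The interval matters because the study is estimation only. SAP 5 specifies no hypotheses or p-values, and SAP 8.4.1 intends a qualitative comparison with published rates. The one published series that the protocol describes (67 of 349 resections, 19%; Protocol 1.0) is titled in the reference list as a single-institution experience. Variation between institutions therefore bears directly on how such a comparison is read. If the rate varies by site, the reported interval would suggest more precision than the data hold.

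**Working it through.** **Inputs from the documents.** N = 165; up to 12 sites, so 165/12 = 13.75 subjects per site if all enrol equally; a planned maximum of 20% per site, 0.20 × 165 = 33 (Protocol 3.2, SAP 1.2), which may be exceeded with Sponsor approval (Protocol 3.2); expected rate 15% to 20%.

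**Assumptions.** The ICC is not given; the range used is 0 to 0.10. Site sizes are not given either. Two layouts of 12 sites are used:
- Layout A, near-equal: nine sites of 14 and three of 13.
- Layout B, unequal, with the largest at the cap: 33, 30, 24, 18, 15, 12, 10, 8, 6, 4, 3, 2.

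**Step 1. The plan's own figure.** One-sided 95% margin = 1.645 × √(p(1−p)/165). At p = 0.20 this is 1.645 × √(0.16/165) = 5.12 points; at p = 0.15 it is 4.57. The stated 5.1% reproduces, and it does so under independence.

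**Step 2. The planned interval.** For 33/165 (20%), Clopper-Pearson gives 14.2% to 26.9%, a half-width of 6.4 points. That this exceeds 5.1 reflects two sides against one and exact against normal limits, which is a separate matter from clustering.

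**Step 3. Design effect.** DE = 1 + (m_eff − 1) × ICC, with m_eff = Σm²/Σm. Layout A: 2271/165 = 13.76. Layout B: 3487/165 = 21.13. Effective N = 165/DE. The margin in the table is 1.645 × √(0.16/effective N), and the interval is the exact one at effective N with a 20% rate.

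**Step 4. Actual coverage of the planned interval.** Site rates were drawn from a beta distribution with mean 20% and the given ICC, site counts were drawn as binomial, and the ordinary Clopper-Pearson interval was computed on the pooled total. Coverage is the share of simulated trials whose interval contains 20%.

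| ICC (assumed) | Layout | DE | Effective N | One-sided margin (points) | Exact interval at effective N | Coverage of planned interval |
|---|---|---|---|---|---|---|
| 0 | A or B | 1.00 | 165 | 5.1 | 14.2-26.9% | 96% |
| 0.01 | A | 1.13 | 146 | 5.4 | 13.8-27.4% | 95% |
| 0.01 | B | 1.20 | 137 | 5.6 | 13.7-27.7% | 94% |
| 0.02 | A | 1.26 | 131 | 5.7 | 13.5-27.9% | 93% |
| 0.02 | B | 1.40 | 118 | 6.1 | 13.2-28.4% | 92% |
| 0.05 | A | 1.64 | 101 | 6.6 | 12.7-29.1% | 89% |
| 0.05 | B | 2.01 | 82 | 7.3 | 12.0-30.3% | 85% |
| 0.10 | A | 2.28 | 72 | 7.7 | 11.5-31.0% | 83% |
| 0.10 | B | 3.01 | 55 | 8.9 | 10.4-33.0% | 76% |

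At a true rate of 15% the coverages are within about one point of these. The exact method's built-in conservatism absorbs an ICC up to about 0.01 when sites are near-equal, and about 0.005 when they are unequal.

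**Step 5. Fewer sites.** The plan says up to 12. With five sites of 33, m_eff = 33. An ICC of 0.01 gives DE 1.32 and coverage of about 93%; an ICC of 0.05 gives DE 2.60, effective N 63 and coverage of about 80%.

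**Step 6. What the ICC values mean.** Between-site SD = √(ICC × 0.20 × 0.80). This is 4.0 points at 0.01, 5.7 at 0.02, 8.9 at 0.05 and 12.6 at 0.10.

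**The case against.** The strongest reply is that nothing in the documents shows that the rate varies by site, and that for little or no clustering the planned interval is sound. This stands. A reader might infer that the interval is definitely too narrow; the documents do not support that. With 12 sites and an ICC of 0.01 or less, coverage stays at about 94-96%, and the values of 0.05 and 0.10 imply large differences between sites (SDs of 8.9 and 12.6 points around 20%).

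Other stronger readings also fail:
- **That the clustering is hidden.** It is untabulated, not hidden. Per-subject listings are planned, and site and surgeon identifiers are in the data.
- **That only a few surgeons operate.** The number of surgeons is not stated; the SAP says only that surgeons do several cases.
- **That the SAP breaks a protocol commitment.** The protocol's center analyses were optional and depended on within-center sample size, and the protocol also planned no adjustment. With about 14 cases per site, declining by-site rates is defensible.
- **That this is the only interval reported.** Tables 18 to 28 follow the Table 7 format and so also carry exact intervals.
- **That error rates or a decision are affected.** There is no test, success criterion or threshold, and the literature comparison is qualitative.

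It is also fair that the 20% cap limits concentration, and that an ICC from so few sites is poorly estimated. In simulation with 12 near-equal sites at a 20% rate, the usual analysis-of-variance estimate ranged (5th to 95th percentile) from about −0.04 to 0.06 when the true ICC was 0, and from −0.02 to 0.14 when it was 0.05.

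What the reply does not remove is that the plan assumes independence for the primary interval while recognising repeated surgeons and possible site effects, and provides no summary by which to judge that assumption.

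**Conclusion.** The point holds in conditional form. The primary interval and the stated margin of error assume independent subjects, and the interval will be too narrow if the issue rate varies between sites or surgeons. With 12 sites and a 20% rate, the loss ranges from negligible (coverage about 94-96% at an ICC of 0 to 0.01) through modest (92-93% at 0.02) to material (85-89% at 0.05, 76-83% at 0.10). The ICC values and the site sizes are assumptions. Fewer sites, or a site above the cap, would make the loss larger.

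The consequence is limited to possibly overstated precision in a descriptive comparison with the 15-20% range. That makes this an inexpensive improvement worth making, not a flaw that undermines the study.

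**What to change.** 1. **SAP 8.4.1.** Keep Clopper-Pearson as the primary interval. Add one sensitivity 95% interval for the primary percentage that allows for clustering by site. Two options are a beta-binomial interval, or an exact interval on the effective sample size with the estimated design effect not allowed below 1. Name the method before the analysis is run. Repeat it with surgeon within site as the cluster, as a check.
2. **SAP 8.9.** Replace the sentence that rules out site summaries with one table for the Full Analysis Set: number of subjects with a stapler performance issue, number with an anastomosis attempted, and percentage, by site.
3. **SAP 7.** Add that the stated margin assumes independent subjects.

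**Cost.** Some SAP wording, one interval with its check, and one table; no new data, since site and surgeon initials are already used for Table 6. The downsides are that the sensitivity interval may be wider than the primary one, and that any ICC from 12 or fewer sites is imprecise. If an ICC is reported it should be labelled as such; otherwise it can be omitted, because the by-site table is informative without it.
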